On rare occasions, development of a serotonin syndrome or neuroleptic malignant syndrome-like events have been reported in association with treatment of fluoxetine, particularly when given in combination with other serotonergic (among others, L-tryptophan) and/or neuroleptic drugs. As these syndromes may result in potentially life-threatening conditions, treatment with fluoxetine should be discontinued if such events (characterised by clusters of symptoms, such as hyperthermia, rigidity, myoclonus, autonomic instability with possible rapid fluctuations of vital signs, mental status changes, including confusion, irritability, extreme agitation, progressing to delirium and coma) occur and supportive symptomatic treatment should be initiated. The risk of this is very low and was not reported in the two phase IIa clinical studies of fluoxetine in multiple sclerosis.^{18, 20}

Drug withdrawal: The SPC reports that withdrawal symptoms when treatment is discontinued are common, particularly if discontinuation is abrupt. In previous phase IIa clinical studies of fluoxetine in multiple sclerosis ¹⁸ ²⁰ they did not report any withdrawal reactions upon discontinuation of long term use of Fluoxetine. Based on these previous studies^{18, 20}, gradual dose reduction in this protocol will not occur on the last treatment visit, however, participants will be followed by telephone 1 month after terminating the study to ascertain any issues with terminating the medication Participants are also reminded in the Participant Information Leaflet (PIL) to contact the study team if there are any withdrawal symptoms.

Risk minimisation: standard monitoring and treatment of nausea, diarrhoea and headache will be provided as needed. Patients with renal failure or hepatic failure are excluded from the trial. If clinically significant LFT changes occur during the trial, or creatinine>130mmol/l, the steps outlined in section 6.7.3 (Management of Laboratory Abnormalities) will be followed. FBC monitoring (including neutrophil count) is part of the safety blood panel, and the steps outlined in section 6.7.3 will take place if the neutrophil level falls below <1.0 x10⁹ /l or the platelet level reduces to <50 x10⁹ /l.

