3 STUDY DESIGN

MS-SMART is a multicentre, multi-arm, double blind, placebo-controlled phase IIb randomised controlled trial. A total of 440 patients with SPMS, with an entry criteria of an EDSS score of 4.0-6.5 will be equally randomised to receive placebo or one of the three active agents (amiloride 5mg bd, riluzole 50mg bd and fluoxetine 20mg bd). Patients will be followed up for 96 weeks with outcomedata collected after 0, 24, 48 and 96 weeks (see flowchart below). That is, the duration of the trial for a trial participant is 96 weeks (a telephone assessment at week 100, 4 weeks post completion will be conducted). This is standard practice for phase II trials in SPMS.

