Visit Number 8:

Week 72 (+/- 2 weeks) Trial participants return to the research clinic and the following assessments will be completed: safety bloods (Cr&E,FBC, Hb, LFT inc. [¥]GT, serum biomarkers [UCL]) compliance assessment relapse assessment (count/grade) adverse events concomitant medication

The next MRI appointment is booked.

Trial participants will receive their next prescription.

Anticipated visit duration = 20 minutes.

CSF Neurofilament Sub-study

Patients consented to the CSF neurofilament and CSF lymphocyte phenotyping sub study will have their blood and urine sampled +/- 14 days of visit 8.

Visit Number 9: Week 96 (+2 weeks)

End of Study MRI:

Core brain MRI

Core brain MRI will be completed at this visit (or within 7days prior to visit 9). WOCBP will have a urine pregnancy test prior to their MRI, compliant with National Guidelines for MRI.

Advanced MRI, CSF Neurofilament and CSF lymphocyte phenotyping and OCT Sub-studies Those participants that have consented to additional MRI imaging (advanced MRI) and/or CSF, blood and urine Neurofilament and CSF lymphocyte phenotyping and/or Optical Coherence Tomography (OCT) will have these assessments completed at this visit (or within 7 days prior to visit 9).

END OF TREATMENT SCHEDULE

Trial participants finish their study medication and the following assessments will be completed:

- safety bloods (Cr&E,FBC,Hb, LFT inc. ^xGT, serum biomarkers [UCL])
- compliance assessment
- relapse assessment (count/grade)

Sponsor No.12/0219 v7 Page **51** of **73**

- adverse events
- concomitant medication
- physical examination
- vital signs
- blinding questionnaire

They will undertake the following assessments *EDSS [assessing physician] MS Functional Composite (MSFC - 9HPT,25TFW,PASAT) Symbol Digit Modalities Test (SDMT) Sloan Low contrast visual acuity (SLCVA) Multiple Sclerosis Impact Scale v2 (MSIS29) Multiple Sclerosis Walking Scale v2 (MSWS) NFI NPRS and BPI Health economic questionnaire (EQ-5D)

*A telephone EDSS assessment (assessing physician or nurse) is permissible if the participant is unable to attend clinic, however the participant should attend their appointments wherever possible and the EDSS be conducted face-to-face.

Anticipated visit duration = 60 minutes.

Telephone Follow up:

Week 100 (+/- 4 days)

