Trial participants will be contacted by telephone to monitor for any AEs occurring within 30 days following completion of trial medication. AEs occurring in the follow up period are to be reported as outlined in section 10.

The patients will then exit the study and their usual best medical care will resume.

Unscheduled visits

Participants will be instructed to contact the local study team between scheduled visits should they suspect a relapse. The proforma shown in appendix 4 will be completed and recorded in the CRF. An unscheduled visit (either for or not for a relapse) can occur at the local study team's discretion and the following will be assessed and recorded: review of current medical and MS history physical examination vital signs safety bloods at PI discretion relapse assessment (as per appendix 4) concomitant medication adverse events

Missed visits

It is vital that participants attend all clinic visits as scheduled. In the event that a visit cannot be re-scheduled the following measures may be taken:

- Concomitant medication and adverse event assessment by telephone
- Questionnaires are due at Visit 7 and 9 and may be sent to the participant for completion (please note this does not apply to the baseline questionnaires. Baseline questionnaires must be completed in clinic)
- Visit 7 and 9 telephone EDSS assessment as outlined above

Please note that these measures apply to participants on treatment and those off treatment and in follow up.

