10.2 DETECTING AEs AND SAEs

All AEs will be recorded in the medical records from the time a participant signs the consent form to take part in the study until study exit (Week 100).

Participants will be asked about the occurrence of AEs/SAEs at every visit during the study. Open-ended and non-leading verbal questioning of the participant will be used to enquire about AE/SAE occurrence. Participants will also be asked if they have been admitted to hospital, had any accidents, used any new medicines or changed concomitant medication regimens. AE data is also available from information written by the participant on the participant diary (this is considered source data). If there is any doubt as to whether a clinical observation is an AE, the event will be recorded.

AEs and SAEs may also be identified by support departments e.g. laboratory values.

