10.3 RECORDING AEs AND SAEs

Collection, recording and reporting of adverse events (including serious and non-serious events and reactions) to the sponsor will be completed according to the sponsor's SOP(INV/S05).

When an AE/SAE occurs, it is the responsibility of the Investigator to review all documentation (e.g. hospital notes, laboratory and diagnostic reports) related to the event. The Investigator will then record all relevant information on the AE log in the CRF and on the SAE form (if the AE meets the criteria of serious). However, if the AE is non-serious (see section 10.1 for serious criteria definition) or MS related (see section 10.4.6.1 for MS expected adverse events) these will remain in the source data (Medical records and Participant diary cards) only. Information to be

Sponsor No.12/0219 v7 Page **57** of **73** collected includes dose, type of event, onset date, Investigator assessment of severity and causality, date of resolution as well as treatment required, investigations needed and outcome.

Clinically significant abnormalities in the results of objective tests (e.g. laboratory variables) will also be recorded as adverse events on the AE log in the CRF, and if are not expected as part of disease or IMP, these will be recorded as unexpected.

All adverse events will be recorded with clinical symptoms and accompanied with a simple, brief description of the event, including dates as appropriate.

All adverse events will be recorded until 4 weeks after the last clinical visit (study exit, visit 10) All Serious Adverse Events will be reportable to the sponsor up to 30 days post last IMP administration.

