14.6 CONTINUATION OF DRUG FOLLOWING THE END OF STUDY

Trial medication will be discontinued after the final clinic assessment for each participant.

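### The only scheduled contact after treatment has conflicting anchors; on the schedule's anchor it can fall 10 to 18 days after the last dose, although it is meant to monitor 30 days

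*Protocol*

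**What the plan says.** The final treatment visit is given in section 7.2 as "Visit Number 9: Week 96 (+2 weeks"), so it may fall up to two weeks late but not early. Participants finish study drug there, and section 14.6 confirms it: "Trial medication will be discontinued after the final clinic assessment for each participant". A late visit 9 therefore means a late last dose.

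One scheduled contact follows, the telephone call, after which the participant leaves the study. Its timing and the end of adverse event (AE) recording are described in two ways.

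- **By study week.** Section 7.2 and its schedule of events put the call at "Week 100 (+/- 4 days"). Section 10.2 collects AEs "until study exit (Week 100"). The synopsis gives 100 weeks per participant.
- **By time since treatment or the last visit.** Section 1.2.2.1 (drug withdrawal) says "participants will be followed by telephone 1 month after terminating the study to ascertain any issues with terminating the medication". Section 10.3 says "All adverse events will be recorded until 4 weeks after the last clinical visit (study exit, visit 10"). The telephone follow-up text in section 7.2 says "Trial participants will be contacted by telephone to monitor for any AEs occurring within 30 days following completion of trial medication", and section 10.6 also refers to a 30-day period after medication.

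Section 3 uses both at once: "a telephone assessment at week 100, 4 weeks post completion will be conducted".

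**The concern.** Week 100 equals 4 weeks after completion only when visit 9 takes place at week 96. The protocol allows it up to week 98 but does not say that the call moves with it. A site that follows the schedule can make the call, close AE recording and exit a participant well before day 30 without any protocol deviation. Another site, following sections 3 and 10.3, would call about two weeks later for the same visit date.

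The call has a specific job. Section 1.2.2.1 explains that there will be no taper at the last treatment visit and relies on the call to detect problems with stopping. It notes that the product information lists withdrawal symptoms as common, particularly after abrupt discontinuation. It also notes that the earlier fluoxetine studies in MS reported none, so the size of the risk is uncertain. After an early call, non-serious events are picked up only if the participant volunteers them, and the end of AE recording can differ between sites.

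The point concerns participants still on drug at visit 9. Those who stop earlier have later visits at which AEs are collected.

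**Working it through.** **Inputs (protocol)**
- Visit 9: week 96 to week 98 (section 7.2).
- Last dose: at visit 9 (sections 7.2 and 14.6).
- Call: week 100, plus or minus 4 days (section 7.2 and schedule of events).
- Period the call should monitor: 30 days after completion of medication (section 7.2).

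**The protocol's own figure.** Section 3 equates week 100 with 4 weeks after completion. (100 − 96) × 7 = 28 days, so this reproduces, but only for visit 9 at week 96 exactly.

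**Study-week anchor.** In study days, week 96 = 96 × 7 = 672, week 98 = 686 and week 100 = 700. The call window is 700 ± 4, i.e. days 696 to 704. If visit 9 is *d* days late (0 to 14), the last dose is on day 672 + *d*, and the call comes

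696 − (672 + *d*) = 24 − *d* to 704 − (672 + *d*) = 32 − *d* days after it.

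| Visit 9 | *d* | Call, days after last dose | Days short of 30 |
|---|---|---|---|
| Week 96 | 0 | 24 to 32 | 6 short to 2 beyond |
| 3 days late | 3 | 21 to 29 | 1 to 9 |
| Week 97 | 7 | 17 to 25 | 5 to 13 |
| Week 98 | 14 | 10 to 18 | 12 to 20 |

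An in-window call reaches day 30 only if 32 − *d* ≥ 30, i.e. *d* ≤ 2.

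**Last-visit anchor.** Visit 9 plus 4 weeks, keeping the 4-day tolerance, gives 28 ± 4 = days 24 to 32 wherever visit 9 falls. Days 24 to 29 are 1 to 6 days short of 30.

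**End of AE recording, visit 9 at week 98.** Section 10.2 at nominal week 100 gives 700 − 686 = 14 days after the last dose. Section 10.3 gives 28 days.

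**The case against.** The best reply is that week 100 is a nominal label. Section 3 explains it as 4 weeks after completion, section 10.3 times study exit from the last clinic visit, and sections 1.2.2.1 and 7.2 tie the call to stopping. On that reading the call falls on days 24 to 32 whatever the date of visit 9, a shortfall of at most 6 days that could pass as ordinary window tolerance. Sections 10.2 and 10.3 both end recording at study exit and would then differ only in label.

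There are also safeguards. The information leaflet reminds participants to contact the team about withdrawal symptoms (section 1.2.2.1), and section 10.4.6.1 tells them to report any symptoms. SAEs stay reportable for 30 days after the last dose (sections 10.3 and 10.5). Section 10.3 keeps non-serious events in source records only, although section 10.4.6.1 reads more broadly, so little that an early call missed might have reached the CRF AE log anyway. The documents give no onset time for withdrawal symptoms, so no missed event is demonstrated. Recruitment is complete and this version is dated 4 June 2018, so a change helps only participants who have not yet exited.

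These points limit the consequence, and several stand in full. They do not remove the conflict. The nominal reading is possible, but neither the schedule nor section 10.2 states it, and it still permits a call before day 30. The safeguards for non-serious events depend on the participant taking the initiative and add no scheduled contact.

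**Conclusion.** The point holds. The protocol gives two anchors for the one post-treatment contact and for the end of AE recording. They agree only when visit 9 is at or very near week 96, and neither ensures the 30 days that the call is said to monitor. On the schedule's anchor, the worst compliant case is a call 10 to 18 days after the last dose, with 12 to 20 days lacking scheduled contact. On the anchor more favourable to the protocol, the shortfall is at most 6 days.

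This assumes that the last dose is taken on the day of visit 9 and that week 100 is counted from baseline. The protocol gives no distribution of visit 9 dates, so the number of participants affected is unknown. Capture of events after an early call becomes passive but does not cease, and the primary analysis is unaffected. The contradiction should be corrected; it does not threaten the trial's main conclusion.

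**What to change.** Use one anchor throughout: the synopsis, sections 1.2.2.1 and 3, section 7.2 (schedule, visit 9 and telephone follow-up), and sections 10.2 and 10.3. For participants treated to visit 9, set the call, the end of AE recording and study exit at the actual last dose plus 30 days, with no early window, for example 0 to +7 days. Simply rewording week 100 as 4 weeks after visit 9 would settle the anchor but leave days 24 to 29 open.

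The 100-week duration in the synopsis then needs to change. Exit would fall between day 672 + 30 = 702 (week 100 + 2 days) and day 686 + 37 = 723 (week 103 + 2 days).

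The cost is an amendment to the wording and one re-dated call, with no new visit or staff. Relative to the present window, exit moves:
- for visit 9 at week 98, 716 − 704 = 12 to 723 − 696 = 27 days later;
- for visit 9 at week 96, from 2 days earlier (702 − 704) to 13 days later (709 − 696).

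The last participant's exit should be checked against the 31.10.2018 end date in the synopsis.

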7.2 STUDY ASSESSMENTS

The Schedule of Events below provides details of all assessments.

	MS-SMAF	RT Sche	dule of E	Events										
MC CMADTClinic Visit Number	0		1	2	3	4	5	6	7	8		9		
Version 6 5 th October 2017 Visit Type	Screening	Baseline MRI Visit	Baseline	Titration							End of Study MRI {must be done while on IMP]	End of study	Follow- up (Tel.)	Unscheduled visit
			Wk 0	Wk 4	Wk 8	Wk 12	Wk 24	Wk 36	Wk 48	Wk 72	Wk 96	Wk 96	Wk 100	
Window				+/- 1wks	+/- 1wks	+/- 1wks	+/- 2wks	+/- 2wks	+/- 2wks	+/- 2wks		+2 weeks	+/- 4 days	
Informed consent	x													
Inclusion/exclusion criteria review	x		х											
Demography	x													
Review of medical and MS History	x													x
EDSS - Review [Treating physician]	x													
EDSS – [Assessing physician]			х						х			x		
Physical Examination	x								x			x		x
Vital signs	x								x			x		x
Safety bloods CR&E, FBC, LFT (inc.GammaGT)†	x			x	x	x	x	x	x	x		x		xd
Urine pregnancy test†		ха	ха				xa,e					xa,e		
Book MRI	x					х				х				
Core MRI		xb					х				xc			
Compliance assessment				x	x	х	х	x	х	х		x		
Relapse assessment (count / grade)	x		x	x	x	х	x	x	x	x		x		x
Adverse events			х	x	x	x	x	x	x	x		x	x	x
Concomitant Medication	x		х	x	x	х	x	х	х	x		x		x
Randomisation			х											
Prescription issued			xf	x	x	х	х	x	х	х				
Drug up-titration				x										
Follow-up													х	
Blinding Questionnaire												x		
MSFC (9HTP, 25TFW, PASAT)			х						х			x		
SDMT			х						х			x		
SLCVA			х						x			x		

MSIS-29v2		x			x		х	
MSWSv2		x			х		x	
NFI - PRO		x			х		x	
NPRS, NPS and BPI		х			х		х	
EQ-5D		х			х		х	
BDI	х							

Clinic Visit Number	0		1	2	3	4	5	6	7	8		9		
Visit Type	Screening	Baseline MRI Visit	Baseline	Titration							End of study MRI	End of study	Follow- up (Tel.)	Unsheduled visit
			Wk 0	Wk 4	Wk 8	Wk 12	Wk 24	Wk 36	Wk 48	Wk 72		Wk 96	Wk 100	
Window				+/- 1wks	+/- 1wks	+/- 1wks	+/- 2wks	+/- 2wks	+/- 2wks	+/- 2wks		+2wks	+/- 4 days	
OCT (subgroup)			xg									xc		
CSF Neurofilament/lymphocytes (subgroup) Lumbar puncture††			xg						x			хс		
CSF Neurofilament/lymphocytes (subgroup) Blood & urine samples††			xg			x	x		x	x		хс		
Advanced MRI (subgroup)		x										х		x
Staff Present														x
Treating Neurologist	у								у			у		x
Independent Assessing Neurologist			У						у			у		
Study Nurse	у		у	у	У	у	У	у	у	у		у		xd

Notes				
a= must occur prior to MRI and at baseline visit, within 1 week (-7 days) Applies to WOCBP. Repeat testing will be dependent on timing of assessments.				

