9.2.4 Clinical Secondary Outcome Measures

When the change over time in continuous outcomes (EDSS, 9 hole peg test, PASAT, MS functional composite score, Symbol Digit Modalities Test (SDMT), Sloan Low contrast visual acuity (SLCVA), Multiple Sclerosis Impact Scale v2 (MSIS29), Multiple Sclerosis Walking Scale v2 (MSWS), NFI, NPRS, BPI, NPS and health-related quality of life (EQ-5D)) is found to be reasonably normally distributed, perhaps following transformation, these will be compared for active treatments and the placebo groups using normal linear models as in section 9.2.2. If normality cannot be assumed, non-parametric comparison tests will be used. Cox proportional hazard models (adjusting for the minimisation variables) will be used for time to first relapse, timed 25 foot walk and time to progress to a given EDSS score, with the difference between each active treatment and placebo being expressed in terms of a hazard ratio. In exploratory analyses, additional statistical modelling will assess whether composites of imaging and disability measures can be used to predict temporal evolution of SPMS and response to treatment.

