10.4.6 Non Reportable AEs/SAEs/SARs

The following will not be reported on the AE log in the CRF or to the sponsor as AEs/SAEs/SARs

10.4.6.1 Expected events related to SPMS:

SPMS is a progressive neurological condition and as such deterioration in neurological symptoms is expected. Therefore natural changes in motor, sensory, balance, sphincter (including urinary tract infections), visual, cognitive and fatigue levels are excluded as AEs/SAEs/SARs and will not be reported as such. In addition, relapses will not be counted as AEs/SAEs/SARs, but will be collated separately. They will be graded as follows (and see appendix 4):

Grade 1 relapse: relapse not treated with corticosteroids

Grade 2 relapse: relapse treated with corticosteroids, but not requiring hospitalisation Grade 3 relapse: relapse treated with corticosteroids and requiring in-patient hospitalisation; or relapse not treated with corticosteroids but requiring in-patient hospitalisation

If the participant feels they are experiencing a relapse, they should contact their local MS team (nurse/consultant) or General Practitioner as per routine practice, so that appropriate management can occur. They should also inform the MS-SMART team at their next scheduled visit, so that the relapse can be documented as per appendix 4. At the Investigator's/nurse's discretion the patient can attend for an unscheduled visit, see section 7.

If however, the investigators suspects that the disease has progressed faster due to the administration of the IMP, then they will report this as an unexpected adverse event (important medical event) to the sponsor.

All laboratory values will be recorded on the appropriate pages of the CRF. When there is a shift of a solitary, or group of values during the course of the study, which in the opinion of the Investigator may be classed as serious (life-threatening) and may or may not be deemed

> Sponsor No.12/0219 v7 Page **60** of **73**

attributable to the medication, this finding must be notified to the sponsor immediately. In these instances, the patient will be treated appropriately without regard to the confines of the protocol.

Full details of contraindications and side effects that have been reported following administration of the IMP can be found in the relevant Summary of Product Characteristics (SmPC).

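### If the final visit (week 96) is missed, neither the telephone substitute nor the week-100 call includes a relapse assessment, so relapses after the last attended visit rest on self-report

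*Protocol*

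**What the plan says.** Relapse rate is one of the clinical secondary outcomes in Protocol section 2.2.2.2, and section 9.2.4 plans its analysis: "Cox proportional hazard models (adjusting for the minimisation variables) will be used for time to first relapse". The schedule of events in section 7.2 carries a row headed "Relapse assessment (count / grade)", marked at screening, at baseline and at every clinic visit from week 4 to week 96. The row is blank at the week-100 telephone contact.

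Under Missed visits, section 7.2 says: "In the event that a visit cannot be re-scheduled the following measures may be taken". Three measures follow:
- "Concomitant medication and adverse event assessment by telephone";
- posting of the questionnaires due at visits 7 and 9;
- "Visit 7 and 9 telephone EDSS assessment as outlined above".

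The list applies to participants on treatment and to those off treatment but still followed. Of the week-100 call the section says: "Trial participants will be contacted by telephone to monitor for any AEs occurring within 30 days following completion of trial medication".

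Section 10.4.6.1 separates relapses from adverse events: "relapses will not be counted as AEs/SAEs/SARs, but will be collated separately".

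Two places describe how a participant reports a relapse. Section 7.2, Unscheduled visits, says: "Participants will be instructed to contact the local study team between scheduled visits should they suspect a relapse", after which the appendix 4 proforma is filled in and entered in the CRF. Section 10.4.6.1 instead sends the participant to the local MS team or general practitioner, and has them tell the trial team when they next attend a scheduled visit.

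**The concern.** The missed-visit list rescues several secondary outcomes by telephone or post, but not relapse, which could be asked about on the same call. For visits 2 to 8 this does little harm, because the next attended visit includes a relapse assessment and can catch up. Visit 9 has no successor except the week-100 call, which is an adverse event call.

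Relapse ascertainment therefore depends on attendance. Participants who attend at week 96 are asked directly about relapses. Those who do not attend are counted only if they came forward themselves or if a question on another subject brings the relapse to light. People who cannot attend may well include some who are relapsing or worsening, so the events lost need not be a random sample.

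**Working it through.** The protocol states no figure for this point, so there is none to reproduce. The check has two parts: the text side by side, then a bound on the size.

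**Contacts that could pick up a relapse between week 72 and week 96**

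| Contact | Relapse asked about? | Source |
|---|---|---|
| Visit 9 attended | Yes, count and grade | 7.2, schedule and visit 9 list |
| Visit 9 replaced: medication and adverse event call | Not listed; relapses are not adverse events | 7.2 Missed visits; 10.4.6.1 |
| Visit 9 replaced: telephone EDSS, posted questionnaires | Not described as recording relapses | 7.2 Missed visits |
| Week-100 call | No; directed at adverse events after the end of medication | 7.2 Telephone Follow up; schedule row blank |
| Participant contacts the study team | Yes, proforma into the CRF, if the participant starts it | 7.2 Unscheduled visits |
| Participant tells the team at the next scheduled visit | Not possible when visit 9 is the missed visit | 10.4.6.1 |

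**What the other questions recover, by relapse grade (10.4.6.1)**
- Grade 2 (corticosteroids, no admission): likely to surface through the concomitant medication question.
- Grade 3 (in-patient admission): likely to surface through the admission question in section 10.2. That section is written around visits, so I assume the telephone enquiry follows the same pattern.
- Grade 1 (no corticosteroids): neither question reveals it. It is caught only if the participant reports it.

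**Size**

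Inputs from the protocol: 440 participants, 96 weeks of follow-up, last relapse assessment before the final visit at week 72.

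Assumptions, since the protocol gives neither figure: 5% to 10% of participants miss visit 9 but are telephoned; relapse rate 0.1 to 0.3 per year.

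- Interval without active enquiry: 96 − 72 = 24 weeks; 24/96 = 25% of an affected participant's follow-up. If visit 8 was also replaced by telephone: 96 − 48 = 48 weeks; 48/96 = 50%.
- Share of planned person-time: 0.05 × 0.25 = 1.25%; 0.10 × 0.25 = 2.5%. If every affected participant had also missed visit 8, these double to 2.5% and 5%.
- Planned person-years: 440 × 96/52 = 812.
- Person-years without active enquiry: 440 × 0.05 × 24/52 = 10.2; 440 × 0.10 × 24/52 = 20.3.
- Relapses expected in that time: 10.2 × 0.1 = 1.0 to 20.3 × 0.3 = 6.1.

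The last line counts all relapses expected in the interval, not relapses missed. It is a ceiling that assumes nothing is recovered by self-report, medication or admission questions.

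**The case against.** The strongest reply is that relapses are still collected. Section 7.2 has a standing instruction to contact the study team about a suspected relapse, with the proforma then recorded in the CRF, and this does not depend on attending a visit. It stands against the stronger reading that relapses before a missed final visit go uncollected, which a reader might infer from the list alone. What is lost is scheduled, direct questioning. The instruction does not close that gap, because the participant must start the contact and because section 10.4.6.1 describes another route that ends at a visit that will not take place.

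The list is also permissive. It does not forbid asking about relapse, and section 8.1 has trial-unit staff pursuing missing data with sites. That is fair, but a site that follows the list as written has no prompt to ask.

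A reader might further infer that such participants would be analysed as relapse-free to week 96. The protocol does not say so. Section 9.2.4 sets no censoring rule, and section 9.2.6 leaves derived variables and missing data to the SAP, which is not at hand. Nor is there any sign in this double-blind trial that the loss would differ between arms.

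The compliance assessment is missing from the same list, but the primary analysis is by intention to treat irrespective of treatment taken (section 6.5), and I see no consequence worth pressing.

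The assumed 5% to 10% may be too high. Section 5.5.3 stresses the week-96 MRI for everyone not withdrawn, and that scan falls at visit 9 or within the 7 days before it. The 10% drop-out in section 9.1.1 concerns people leaving the trial and does not inform this figure. Finally, appendix 4 is not in the text supplied, so any telephone procedure it contains could not be checked.

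**Conclusion.** The point holds as a gap in active ascertainment after a missed final visit. In that case no listed substitute and no later scheduled contact includes a relapse enquiry, although relapse rate is a named secondary outcome. Capture then rests on self-report, with the medication and admission questions recovering mainly Grade 2 and 3 relapses and leaving Grade 1 most exposed. The two descriptions of the self-report route differ and need to be reconciled.

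The effect is small. The bound of 1.25% to 2.5% of planned person-time rests on the assumed 5% to 10% missing visit 9, with visit 8 attended, and on no recovery by other routes. The primary outcome is not affected. This is a cheap improvement and does not threaten the trial's conclusions.

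**What to change.** In section 7.2, Missed visits, add relapse count and grade, recorded on the appendix 4 proforma, to the telephone bullet. In the same section and in the schedule of events, add to the week-100 call a relapse enquiry covering the period up to week 96, for anyone who missed visit 9. Reconcile the relapse-reporting instructions in sections 7.2 and 10.4.6.1, so that a relapse reaches the trial team even when no scheduled visit remains.

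The cost is a few lines of text and a minute or two on calls already being made. It needs no extra visits or staff.
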